## 7. STUDY PROCEDURES

---

### 7.1. Study Procedures

The study consists of 5 stages, including the familiarization period and the screening, pre-study and testing, performed on the same day:

- Familiarization Period.
- Screening.
- Pre-study.
- Quality Control.
- Testing.
- Post-Testing.

- Stage I – Familiarization Period

Evaluating an analytical method requires sufficient time for the operators to become familiar with the device operation and the study protocol, and the standard therefore recommends a study familiarization period. During the familiarization period, the operators of the test and comparative method will become familiar with all aspects of set-up, operation, maintenance, quality control, and troubleshooting of both methods. This period will precede the study evaluation process and will coincide with the manufacturer's training performed during the Site Initiation Visit (SIV). During the SIV and familiarization period, routine laboratory quality control procedures will be run and up to 15 subjects will participate in a study simulation to ensure familiarity with the study protocol and all study procedures. After the SIV and familiarization period, the usability study will begin. The test results from the subjects participating in the simulation study during the SIV and familiarization period will not be included in the final study results or the study statistical analyses.

- Stage II – Screening

Potential candidates will receive complete information describing the study and their role and will be encouraged to ask any questions regarding the study. The risks and requirements of this clinical research trial will be explained to each potential subject. Those volunteering to take part will read and sign the Informed Consent Form for participation in the clinical trial before any

study-related procedures are performed. The Informed consent signing will be in front of a study personnel, the principal investigator will review and will sign all source documents, informed consents, and results once a day.

Upon obtaining the signed informed consent, inclusion and exclusion criteria will be reviewed to verify the subjects' eligibility.

- Stage III – Pre-study

Subjects who were found eligible to participate in the study and signed informed consent will be enrolled into the study and assigned a subject ID number, which will be used along with their initials for study record identification.

Designated eSource forms will be completed with the subject's general details, including demographics, medical history, diagnosis and concomitant medications.

- Stage IV – Quality Control

Before each testing day, Quality Control will be performed using the YD Diagnostics - supplied Level 1 and Level 2 Control solutions on all phones used in the study, using two strips from one lot that will be randomly selected.

1. The professional user will use Level 1 Control solution to perform the QC test.
2. The professional user will open the ACR | U.S. application on either the iPhone 11 or Google Pixel 3a device.
3. Following the in-app instructions, the professional user will remove one strip and pipette the Level 1 control solution on the strip. The ACR | U.S. application will guide the user to scan the strip, uploading the data to the backend server for analysis.
4. The professional user will then remove another strip, pipette Level 1 Control solution on the strip and scan it using the Optima device.
5. The professional user will repeat steps 2-4, substituting the Level 1 Control solution with Level 2 Control solution, and between the smartphone devices.
6. The Quality Control will be considered as passing if the ACR | U.S. and the Optima reports the acceptable range as determined by the manufacturer.
7. If the Quality Control test for either phone fails, the error will be identified, and the Quality Control procedure will be conducted again.

- Stage V – Testing
  - 1) The subject will perform the usability study tasks in a simulated home environment, e.g. in a dedicated and isolated room in the clinic simulating a home, where internet connection is available, and a restroom is nearby. The clinic will be set up so that the self-testing will allow the subject to perform the urinalysis test without outside influence and to simulate the home-use testing of the device.
  - 2) The subject will be placed in the private room, with restroom accessibility and internet connectivity, to perform the urinalysis test and complete the task list found below. No training, assistance, feedback, or supplemental instructional materials, other than those described, will be provided to participants. The healthcare professional or other site staff will not be allowed to intervene or answer questions from the subjects during testing, although a 1-800 or clinical assistance phone number, which will be provided to the subject in actual use, will be made available to the subject in case contact is attempted by the subject.
  - 3) The room will be prepared with a desk and chair. The ACR | U.S., in its original packaging will be placed on the desk. The device packaging contains the kit components and the user manual. An in-app instructional guide containing the information most critical to safety and effectiveness is also provided in the form of a readable and understandable, visual, and textual guide on the device App. The patient labeling will be in the format intended for distribution to allow for a realistic evaluation of the labeling effectiveness.
  - 4) The subjects will be asked to follow the device user manual and/or the in-app instructional guide and perform the following tasks:
    - Access the ACR | U.S. App on the smartphone. (iPhone 11 or the Google Pixel 3a)
    - Provide a urine sample in the urine receptacle (to the level marked on the cup) that is included in the ACR | U.S. kit.
    - Immerse the urine strip (provided in the ACR | U.S. kit) in the collected urine specimen for one second.
    - Place the urine strip on the designated area on the Color-Board and wait at least 75 seconds, but not more than 180 seconds.
    - Scan the urine strip and Color-Board with the smartphone App.
    - Send the test results to the study clinician using the smartphone App.
    - Subjects will be asked to complete a questionnaire following completion of the tasks.

[figure not shown]
- 5) Subjects will be observed as they complete the tasks by a research staff member. The research staff observer will complete a dedicated post-test questionnaire.
- 6) Upon completion of the usability study tasks, the subject will provide the urine sample in the device kit urine receptacle to the research staff for further testing. The research staff will perform the urine analysis test using the comparator device, the URiSCAN Optima device. The research staff performing the urine analysis test with the Optima will be blinded to the results of the ACR | U.S. test, until the test with the comparator device is completed.
- 7) Only after the urine has been tested with the Optima, can the subject begin the test with a second kit on the second smartphone device, provided by the operator in the clinic. A new ID number will be given to the second kit, therefore the lab operator will consider this as new urine and will be kept blinded to the urine results.
- 8) The results of the ACR | U.S. and the comparator device (the Optima) will be used for study purposes only and not for diagnostic or therapeutic purposes of patient management. In the case that urinalysis results are required for patient management, urine specimens from the subject will be sent independently to the hospital/clinic laboratory for analysis and only the results of the hospital/clinic urine analysis will be used for patient care and management. The patient will provide only one urine sample for use in both the study and any subsequent clinical urinalysis testing.

- Stage VI – Post-test procedures

Statistical analyses comparing the results from the ACR | U.S. and the Optima will be performed using an appropriate statistical program and methodology.

In compliance with the ICH/GCP guidelines, the investigator/institution will maintain all eSource and all source documents that support the data collected from each patient, as well as all study documents as specified in ICH/GCP Section 8, Essential, Documents for the Conduct of a Clinical Trial, and all study documents as specified by the applicable regulatory requirement(s). The investigator/institution will take measures to prevent accidental or premature destruction of these documents.

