Study Design:	
Eligible subjects meeting the pathological profile will be recruited at the designated site by the study personnel. Following subject consent, the subjects will be evaluated for eligibility based on their health condition and history.
 
The ACR   U.S. kit, in its original packaging, along with the ACR   U.S. smartphone application will be provided to the subject in a simulated home- use environment. All subjects will be provided with a list of tasks to complete, including providing a urine sample and operating the ACR   U.S. device on both an iPhone 11 device and a Google Pixel 3a mobile phone. After completing the test, the lay user will complete a post-test questionnaire. The study observer will also complete a questionnaire to collect information regarding the lay users' use of the ACR   U.S.
 
The device use will be compared with identified risks to determine if the percentage of failures is acceptable. Additionally, measurable usability criteria for specific, critical steps will be evaluated.
 
Following the usability test performed by the lay user, the subjects' urine samples will be tested by the study staff using the URiSCAN Optima Urine Analyzer. These results will be considered as the “true value”.

Data analysis:	
Results from the ACR   U.S. Urine Analysis Test System and the comparator device, the URiSCAN Optima Urine Analyzer, will be presented in tables listing the results in each group and the % exact match (agreement) and the % <math>\pm 1</math> block match.

Study Sponsor:	
Healthy.io Ltd.

Principal Investigators:	
[name] [name], [name],

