### **3. RATIONALE FOR THE STUDY**

---

In addition to the analytical performance tests described above, method comparison and usability tests are crucial steps before companies are permitted to bring such a device to market. All marketed urinalysis devices and urine test strips for home use have performed method comparison and usability studies tested by the intended lay user. Normally in these studies, urine samples are collected and tested by a lay user, using the new home use device, and by a device operator or lab professional using the comparison device. The lay user test results are compared to the results obtained by testing the same urine sample on the comparison device. The method comparison and usability studies provide data on the accuracy and usability of the device, including the lay user's ability to understand and implement the user manual instructions and evaluate the ease of use of the device under actual use conditions (home environment). Moreover, the study provides valuable data originating from unhealthy subjects using mostly their real urine samples and can strengthen the results of the bench analytical tests. The urine samples should be sourced from pathological subjects simulating the "realistic clinical environment" or from healthy subjects, spiked samples to cover the entire color range of the analyte detection reagents.

The ACR | U.S. method comparison study should include similar elements and be designed similarly to previously tested urinalysis analyzers. The study design is meant to demonstrate that the ACR | U.S. may be easily used by a lay person and the results are in agreement with another legally marketed urine analyzer device.

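### As written, lay users are given a task list whose only stated version contains technique and timings, which could cue correct use beyond the manual and app

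*Combined protocol and SAP*

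**What the plan says.** The Study Design part of the synopsis states: "All subjects will be provided with a list of tasks to complete". It describes the contents only broadly, as giving a urine sample and operating the device on both phones.

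Section 7.1, Stage V, step 2 has the subject in a private room "to perform the urinalysis test and complete the task list found below". The same step adds a safeguard: "No training, assistance, feedback, or supplemental instructional materials, other than those described, will be provided to participants". Site staff may not intervene or answer questions.

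Step 4 begins: "The subjects will be asked to follow the device user manual and/or the in-app instructional guide and perform the following tasks". It then lists six device tasks and a closing questionnaire. The strip is to be immersed "in the collected urine specimen for one second", then placed on the Color-Board, where the subject is to "wait at least 75 seconds, but not more than 180 seconds".

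Section 1.2 lists five kit components. A user manual is one of them; a task list is not. Section 3 says that these studies provide data on "the lay user's ability to understand and implement the user manual instructions".

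**The concern.** A usability study of a home device asks whether people given the marketed package, and nothing else, do the right things. A short sheet naming the critical steps in order, with their times, changes that question. A subject who skips or misreads the manual could still follow the sheet correctly, and the observer would record a success that the labeling did not produce.

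The usability results in Sections 8.2 and 10.6 are exposed most directly: percentage completing the device tasks, time-to-completion and requests for assistance. The primary endpoint could also be touched. Section 2.1 names a Timing Flex Study of dipping, assay and wetting times, so the sponsor treats timing as something that might affect the reading. If it does, a sheet that corrects timing could raise block agreement with the Optima above what unprompted users would reach. Cueing of this kind cannot be removed in the analysis.

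**Working it through.** The plan states no figure on this point, so the check sets its passages side by side.

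1. **Does the subject receive a list?** Yes. The synopsis says so for all subjects, and Stage V step 2 has them complete one.

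2. **Which list?** Step 2 points to a list below it. The only one that follows is in step 4.

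3. **How detailed is it?** The six device tasks in step 4 are:

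| Task | Technique detail |
|---|---|
| Open the app | none |
| Provide urine | fill level marked on the cup |
| Immerse the strip | one second |
| Place the strip and wait | designated area; 75 to 180 seconds |
| Scan | none |
| Send the result | none |

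That is 1 + 1 + 2 = 4 technique details, in 3 of the 6 device tasks. Two are timings. The other two refer to marks on the device itself. The list also fixes the order of the steps.

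4. **Does the marketed kit include such a sheet?** Not as a component. Section 1.2 lists a receptacle, strip, absorbing pad, Color-Board and manual. Stage V step 3 likewise puts the packaged kit and manual on the desk.

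5. **Does the safeguard exclude it?** No. Step 2 exempts materials that the protocol describes, and the task list is described in the sentence just before.

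6. **Are the listed tasks the scored tasks?** Largely. Section 10.6 counts app access, urine provision, dipping, strip positioning and taking the picture. It names no dip or wait time. Section 8.2 also uses the term Task List for the critical steps in the risk evaluation, so one term covers both the scoring basis and the subject's material.

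7. **Can the effect be sized?** Let e be the proportion of unprompted users who err on a scored step, and p the share of those errors that the sheet prevents. Observed failure is then e × (1 − p), and completion is overstated by e × p. The documents give neither e nor p. They also give no Timing Flex results and no expected agreement. If the sheet is goal-level, or adds nothing to what users take from the manual and app, p is 0. No numerical range can be derived.

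**The case against.** The strongest reply is that the subject's sheet is not shown. The synopsis describes it in near goal-level terms. The step 4 bullets may be protocol text for sites, since the last one, on the questionnaire, is not phrased as an instruction to a subject. The available text lacks some appendix material and a figure after step 4, so a subject form may exist there. This stands: that subjects see the step 4 wording is the literal reading, but it is not established.

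Three stronger readings are tempting, and the documents do not support them.

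- **That users are coached.** Stage V bars training, assistance, feedback and staff intervention, and step 1 requires testing free of outside influence. What remains is possible cueing by a sheet.
- **That the sheet's content is absent from the marketed product.** Section 1.2 lists components and does not give the manual's text. Section 1.3 describes in-app video, text and sound guidance, and Stage V step 3 says that the app guide carries the most critical information. The same steps and timings may be there. Only the separate sheet is shown to be extra.
- **That the labeling goes untested.** Subjects receive the original packaging and distribution-format labeling, and are told to use the manual and/or app. A sheet could dilute that test, but would not replace it.

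The pass rule in Section 9.1 also limits the effect. It requires a successful Color-Board scan, and a mistimed dip is not shown to count as failure. The app asks for a rescan (Section 1.3) or repositioning of the strip (Section 10.7) when needed.

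These replies limit the size and certainty of the point. They do not remove it, because bars on staff help do not cover a sheet, and whether users obtain the steps from the labeling is what the study is meant to find out.

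**Conclusion.** The point holds as a possible bias in favour of the device. A site following the synopsis and Stage V literally could give lay users step order and timings on a sheet that is not a component of the marketed kit, and nothing in the plan tells it not to. Task completion, time-to-completion and requests for assistance could look better than in unprompted use; agreement with the Optima possibly could too.

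This assumes that the subject's sheet resembles step 4 and that some subjects would rely on it instead of the manual or app. The documents settle neither. Any percentage attached to the effect would be assumption alone, and the effect on the Color-Board pass rule may be small. The point is best classed as a cheap improvement.

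**What to change.** In the synopsis and in Section 7.1, Stage V, steps 2 and 4:

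- State that the subject receives only a goal-level prompt: use the kit and app to test your urine and send the result, as you would at home.
- Keep the step-level list with timings on the observer's scoring form only, and say so. This also separates the two uses of the term Task List.
- State that, before the last scan, no study document other than the marketed labeling (manual and app) shows technique or timing to the subject. The last scan matters because each subject tests on two phones.

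If a subject form already exists, check it against this wording.

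The cost is a few changed sentences and a one-line subject card, with no added visits, staff or subjects. The downside is that observed completion and agreement may look slightly less favourable.

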**Figure 1 – Method Comparison Study Flow**

## 8. SUBJECT COMPLETION / WITHDRAWAL

### 8.1. Accuracy Evaluation

The ACR | U.S. test results will be compared to the Optima test results. The data will be graphically presented to compare the percent exact match (agreement) and the percent  $\pm 1$  block match (agreement) between the ACR | U.S. (tested by the lay user) and the comparator device (tested by a healthcare professional), for the different tested concentrations (blocks).

### 8.2. Usability Evaluation

The usability of the ACR | U.S. will be determined by evaluating the percentage of study subjects able to complete the device related tasks, including operating the ACR | U.S. with minimal attempts to ask for assistance. Measurable usability criteria for specific, critical steps, such as time-to-completion, number of requests for assistance, numerical ratings, etc., will be evaluated by observer evaluation and user questionnaire responses.

The device usability information will be compared to identified device risks. Device and user related hazards were identified and documented in the ACR | U.S. Risk Analysis file. These specific device and user related risks will be evaluated in the usability study, according to the following steps:

- (1) Identify device and user related hazards (Risk Analysis)
- (2) Identify critical steps to be completed (Task List)

- (3) Compare device's use with identified risks (Observer Evaluation and User Questionnaire)
- (4) Apply Criteria - percentage of permissible failures (refer to section 11.6.4)
- (5) Link assessment to the overall risk analysis (study conclusions)

The following measurable usability criteria for specific, critical steps, based on observer evaluation or user questionnaire responses, will be assessed through analysis of the data:

- (1) Time-to-completion of task;
- (2) Number of requests for assistance;
- (3) Numerical ratings describing the participants' level of success in completing tasks will be collected through user posttest questionnaire responses;

Qualitative information regarding specific user errors and inefficiencies will be collected through observer evaluation and user posttest questionnaire responses.

In addition, key system errors will be evaluated in some subjects. Examples of key errors may include the following:

1. Interruption during the test by an incoming phone call.
2. Interruption during the test by an incoming message.
3. No Internet connection

The subject will be required to continue device operation according to the user manual.

## **9. SUBJECT COMPLETION / WITHDRAWAL**

---

### **9.1. Completion**

A subject will be considered to have completed the study if the urine sample has been tested.

A subject will be considered to have passed the usability test if he/she was able to scan the Color-Board successfully. In addition, in case a subject failed in his/her first try but identified the problem alone and requested a second kit, and then completed the test, the subject will be considered to have passed the usability test.

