- **Boundary Study:** Healthy.io designed an experiment to test the physical boundaries (such as the phone's distance and angle in relation to the Color-Board) which would prevent the ACR | U.S. from capturing an accurate image that can be evaluated by the algorithm.
- **Multiple Phones and Operating Systems Study:** Healthy.io designed an experiment to test the ACR | U.S. with multiple smartphone devices and operating systems versions (iOS and Android).
- **Timing Flex Study:** Healthy.io designed an experiment to test the impact of different dipping times, assay-times, and strip wetting times on the ACR | U.S.

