## **10.6. Statistical Analysis**

- General Considerations

Statistical analyses will be performed using an appropriate statistical program and methodology.

Baseline demographic and safety analyses will be performed on all enrolled subjects.

- Demographic and Other Baseline Variables

Demographic and baseline condition related characteristics will be tabulated. Continuous variables will be summarized by a mean, standard deviation, minimum, median and maximum, and categorical variables by a count and percentage.

- Disposition of Subjects

The number and percent of subjects who fail to complete the study and the number and percent of subjects who fail to complete the study because of Adverse Events will be presented.

- Efficacy Analysis

The % exact match (agreement) of the ACR | U.S. compared to the comparator device, for the same Albumin-Creatinine Ratio concentration (block) will be calculated. The %  $\pm 1$  block match (agreement) of the ACR | U.S. compared to the comparator device, for the same Albumin-Creatinine Ratio concentration (block) will also be calculated.

- Usability Analysis

The usability of the ACR | U.S. will be determined by evaluating the percentage of study subjects who are able to complete the device-related tasks, including accessing the ACR | U.S. App, providing a urine sample in the urine receptacle, dipping the kit urine strip in the urine specimen, positioning the strip on

the Color-Board and taking a picture using the smartphone App, with minimal attempts to ask for assistance.

Measurable usability criteria for specific, critical steps, such as time-to-completion, number of requests for assistance, numerical ratings, etc., will be evaluated by observer evaluation and user questionnaire responses. Descriptive statistics will be provided for usability criteria.

- Adverse Event

In general, there are no anticipated adverse events in this study; however, if any adverse events do occur they will be recorded and presented in tables.

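### Section 9.1 passes any subject who scans the Color-Board, sections 8.2 and 10.6 count task completion, and the plan does not say which gives the usability percentage

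*Combined protocol and SAP*

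**What the plan says.** Section 10.2 makes usability in lay hands the secondary endpoint but attaches no statistic to it. Four other places bear on what counts as success.

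- **Section 9.1 (Completion)** has the only pass rule at subject level: "A subject will be considered to have passed the usability test if he/she was able to scan the Color-Board successfully". What makes a scan successful is not defined. There is a second route to a pass: "in case a subject failed in his/her first try but identified the problem alone and requested a second kit, and then completed the test".
- **Section 7.1, Stage V, step 4** lists the tasks. The strip is immersed "in the collected urine specimen for one second". The subject then places it on the board and is to "wait at least 75 seconds, but not more than 180 seconds". Two further separate entries follow: "Scan the urine strip and Color-Board with the smartphone App" and "Send the test results to the study clinician using the smartphone App".
- **Section 8.2 (Usability Evaluation)** bases usability on the share of subjects who manage the device tasks with little call for help. It adds time per task, requests for help, ratings, and a qualitative account of user errors from the observer and the questionnaire. For the acceptable failure percentage it refers to section 11.6.4, which I cannot find in the public text.
- **Section 10.6 (Usability Analysis)** uses the same kind of percentage and names app access, giving the sample, dipping, and then positioning the strip on "the Color-Board and taking a picture using the smartphone App, with minimal attempts to ask for assistance".

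**The concern.** The 9.1 rule and the task-completion measure can classify the same subject differently. Someone who leaves the strip in urine too long, or scans well outside the time window, has not done the task as listed but has passed under 9.1 once the app accepts the image. If the percentage in the report is the 9.1 figure, it describes the ability to obtain a scan. Section 3 wants the study to show whether lay users can follow the manual, which is a wider question.

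Because the plan does not choose between the two, the choice could be made after the data are seen. The 9.1 figure would generally be the more favourable one. Section 8.2 also intends to compare use with identified risks at each critical step, and a scan-only pass gives no information by step.

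**Working it through.** The plan states no usability rate, threshold or precision target, so there is no figure to reproduce. The check is mainly a comparison of texts.

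**Step 1. Task list against the two measures.**

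| Device task in 7.1, Stage V, step 4 | Named in the 9.1 rule | Named in the 10.6 list |
|---|---|---|
| Open the app | No | Yes |
| Provide the sample | No | Yes |
| Immerse for one second | No | Dipping yes, duration no |
| Place strip on the board | No | Yes |
| Wait 75 to 180 seconds | No | No |
| Scan | Yes | Yes, as taking a picture |
| Send the result | No | No |

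The 10.6 list is introduced as a set of inclusions, so it is open. It would exclude someone who never dipped the strip. It does not settle a wrong dip time, a wait outside the window or an unsent result.

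**Step 2. Does the app close the gap?** Section 1.3 says the software checks each scan against boundary conditions and asks for another if they are not met. The only description of boundaries, the Boundary Study in 2.1, is physical: phone distance and angle. Section 10.7 adds a prompt to reposition a misplaced strip, so placement is partly covered. No section says that a mistimed or wrongly immersed strip is refused. The gap therefore concerns immersion, wait and, possibly, sending.

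**Step 3. Scale, by assumption only.** N = 250 is the minimum in 6.1. The rest is assumed: scan success s = 98%, and compliance q among those who scan, the same for each of the three steps. The 9.1 rule passes 250 × 0.98 = 245. The number passed despite at least one broken step is:

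- same subjects break all three steps: 245 × (1 − q)
- independent failures: 245 × (1 − q³)
- different subjects break each step: 245 × 3(1 − q)

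| q | Same subjects | Independent | Different subjects | All-step rate, independent (0.98 × q³) |
|---|---|---|---|---|
| 99% | 2.5 | 7.3 | 7.4 | 95.1% |
| 95% | 12.3 | 34.9 | 36.8 | 84.0% |
| 90% | 24.5 | 66.4 | 73.5 | 71.4% |

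If sending happens automatically with the scan, two steps remain. The largest values become 245 × 2(1 − q), which is 4.9, 24.5 and 49.0. If the app does refuse mistimed scans, the numbers fall further.

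**The case against.** The strongest reply is that 9.1 is not shown to be the endpoint definition. Sections 8.2 and 10.6 say how usability is to be determined, an observer watches every subject, and user errors are to be collected. A broken step need not go unrecorded. This stands, and it limits the point to two unreconciled definitions. It does not remove it. The plan still does not say which definition supplies the percentage, and 8.2 treats specific user errors as qualitative information, not as a pass or fail count.

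Sending is the weakest example. Section 1.3 describes a cloud-based algorithm, and the quality-control steps in 7.1 describe scanning as uploading the data. A successful scan may therefore already send the result, although step 4 lists sending as its own task.

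A reader might infer from the Timing Flex Study in 2.1, which is to "test the impact of different dipping times, assay-times, and strip wetting times", that timing errors are the ones most likely to give a wrong ratio. The documents do not support that. No results are given, and the study could equally have shown tolerance. An unsent result would not change the ratio at all.

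It can also be said that scoring every step exactly as instructed is a preference, and that risk-based scoring is legitimate. That is fair. Reporting failures per task and the scan-only figure alongside lets a reader apply either view.

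**Conclusion.** The point holds as a conflict between definitions. Section 9.1 passes on the scan, 8.2 and 10.6 count task completion, and the source of the secondary-endpoint percentage is not fixed. Followed literally, 9.1 classes as passed a subject who departed from the listed immersion or wait, or did not send the result if sending is separate. The 10.6 list does not clearly exclude these cases.

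The size cannot be derived from the documents. The range of about 2 to 74 subjects in 250 rests wholly on assumed rates and on all three steps being separate from the scan.

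A reader might go further and conclude that the usability endpoint is uninformative, or that usability cannot be related to agreement. Neither follows. Task-level data are planned, and observer records may allow the link. The primary endpoint compares the lay user's own result with the comparator, so a use error that changes the reported block already enters that comparison. The primary endpoint is not defined by the 9.1 rule. This is a cheap improvement to a secondary endpoint.

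**What to change.** Reconcile sections 7.1 (Stage V, step 4), 8.2, 9.1 and 10.6 into one definition fixed before data are seen: a subject succeeds if every device task in step 4, from opening the app to sending the result, is completed as instructed, including the stated immersion and wait. Make the 10.6 list match, and say whether sending is a user action or part of the scan.

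Score it from the observer's record, with app time stamps where available. Report failures for each task, and the scan-only percentage, as separate and clearly labelled figures.

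The cost is wording in these sections and slightly more recording by an observer who is already present. The observer form is not in the public text, so some of these items may already be on it. The downside is a probably lower headline usability percentage.
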